4.7 Criteria for Early Study Termination

- 4.7.1 An early stopping rule will be established such that the trial will be terminated if either or both of the following conditions hold:
 - 1. If the highest dose, the 1.2mg/kg dose, moves forward into the phase II portion of the study, and if more than 10% of the participants experience a grade 3 motor or sensory neurotoxicity lasting for more than 4 weeks, the trial will be terminated. The first 10 participants in the phase II portion of the study at the 1.2 mg/kg dose will be monitored for this outcome. If more than 3 out of the 10 participants experience grade 3 neurotoxicity, this will be considered sufficient to stop the trial. With an underlying probability of grade 3 neuropathy of no more than 10%, the probability of observing > 3 participants with grade 3 neuropathy is less than 5%.
 - 2. If any PML case is diagnosed when the CD4 count is above 50, the trial will be terminated.

4.7.2 Request by the protocol chairs, AMC, IRB, NCI, OHRP, or pharmaceutical sponsors.

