5.1.2 Dose Modifications for Pulmonary Toxicity

Pulmonary toxicity will be defined by grade 3 or 4 dyspnea, pneumonitis, and/or hypoxia that persists for at least three days. There must be no evidence of other etiologies, including left atrial hypertension, congestive heart failure, infection, metabolic abnormalities, or cancer related causes (e.g., malignant pericarditis).

Participants who develop pulmonary toxicity associated with brentuximab vedotin may benefit from treatment with corticosteroids. However, there are no published guidelines to suggest the most appropriate dosing or duration of treatment. Administration of 100 mg of oral or intravenous prednisolone in single daily or two divided doses has been reported to improve symptoms in adults with pulmonary toxicity secondary to gemcitabine. The suggested dose for participants who develop pulmonary toxicity is methylprednisolone 1 mg/kg IV every 12 hours for a minimum of seven days. Participants who develop pulmonary toxicity meeting the above definition will be taken off protocol therapy (brentuximab vedotin).

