5.2.6 Neuropathy

Once brentuximab vedotin has been discontinued, participants experiencing Grade 3 vinblastine-neuropathy (e.g., obstipation, weakness) may continue the study receiving AVD with dose adjustments in vinblastine as clinically necessary, based on the level of neuropathy on the day of treatment. Participants experiencing Grade 4 vinblastine neuropathy will have this drug omitted from all future cycles of AVD.

5.2.7 If a participant's weight has changed more than 10% from baseline or the prior dose, the new BSA must be used on the next cycle. For a weight change of 10% or less, doses may be adjusted according to the BSA or remain the same in conjunction with institutional guidelines.

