13.4 Premature discontinuation of the study

The sponsor reserves the right to stop the trial at any time. The investigators will be informed of this decision in writing.

The same applies to any investigator wanting to discontinue his/her participation to the trial. The investigator must immediately inform the sponsor in writing of this decision.

An early stopping rule will be established such that the trial will be terminated if either or both of the following conditions hold:

- 1. If more than 10% of the subjects experience a grade 3 motor or sensory neurotoxicity lasting for more than 4 weeks, the trial will be terminated. The first 10 patients in the phase II portion of the study at the 1.2 mg/kg dose will be monitored for this outcome. If more than 3 out of the first 10 patients in the phase II study experience grade 3 neurotoxicity, this will be considered sufficient to stop the trial. With an underlying probability of grade 3 neuropathy of no more than 10%, the probability of observing > 3 patients with grade 3 neuropathy is less than 5%.
- 2. If any PML case is diagnosed when the CD4 count is above 50, the trial will be terminated.

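### The phase II neurotoxicity stopping rule names grade 3 events only, so read literally it leaves out a participant whose neurotoxicity is recorded only as grade 4

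*Combined protocol and SAP*

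**What the plan says.** AMC protocol, Section 4.7.1 item 1, applies if the 1.2 mg/kg dose goes forward to phase II. It builds the rule in four steps, each worded for grade 3:

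- The general condition for termination is that "more than 10% of the participants experience a grade 3 motor or sensory neurotoxicity lasting for more than 4 weeks".
- The group watched is defined next: "The first 10 participants in the phase II portion of the study at the 1.2 mg/kg dose will be monitored for this outcome".
- The boundary follows: "If more than 3 out of the 10 participants experience grade 3 neurotoxicity, this will be considered sufficient to stop the trial".
- The justification is that, "With an underlying probability of grade 3 neuropathy of no more than 10" percent, "the probability of observing > 3 participants with grade 3 neuropathy is less than 5" percent.

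The French protocol, Section 13.4 item 1, has the same rule in nearly the same words: "If more than 3 out of the first 10 patients in the phase II study experience grade 3 neurotoxicity". The statistical sections of the two protocols (Sections 11 and 16) do not redefine the event.

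Elsewhere the AMC protocol spells out a wider range when it wants one. Section 5.1.2 reads "Pulmonary toxicity will be defined by grade 3 or 4 dyspnea, pneumonitis, and/or hypoxia", and exclusion criterion 3.2.5 covers peripheral neuropathy of grade 2 and above. For neuropathy itself the grades are kept apart. Table 5-A has separate grade 3 and grade 4 rows, and Section 5.2.6 follows its grade 3 instruction with a separate one: "Participants experiencing Grade 4 vinblastine neuropathy will have this drug omitted from all future cycles of AVD".

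**The concern.** A stopping rule for toxicity should respond at least as strongly to worse events. Here the event, the boundary and the probability statement all stop at grade 3, in a document that writes out higher grades where it means them and handles grade 4 neuropathy as its own category. A reader applying the text literally has good grounds to leave a grade 4 participant out of the count.

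The literal text matters because Appendix VII says that stopping a phase II trial for toxicity depends on meeting criteria stated in the protocol, as judged by the Protocol Chair, the Medical Monitor and the Group Statistician. If grade 4 cases occurred, they would either apply a count that omits the most severe events or reinterpret the rule after seeing the data. Section 2.4.5 names overlapping neuropathy from brentuximab vedotin and vinblastine as a concern to be managed, and this is the phase II boundary set up to watch for it.

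**Working it through.** **Inputs from the documents.** n = 10 participants; stop if more than 3, that is 4 or more, have the event; reference rate 10%; stated false-stop probability below 5% (all from 4.7.1 item 1).

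**Formula.** With X the number of participants counted and p the probability that a participant is counted,

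P(stop) = P(X ≥ 4) = 1 − Σ (k = 0 to 3) C(10, k) p^k (1 − p)^(10 − k).

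**The plan's own figure.** At p = 0.10 the four terms are 0.3487, 0.3874, 0.1937 and 0.0574, which sum to 0.9872. So P(stop) = 1 − 0.9872 = 0.0128. The stated bound of 5% is correct. A boundary one lower gives P(X ≥ 3) = 0.0702, so more than 3 is the smallest boundary that stays under 5%. The arithmetic is sound; the problem is the definition of the event.

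**Fixed total rate, varying grade 4 share.** Let π be the total rate of grade 3 or higher and f the share of those participants recorded only at grade 4. The literal count uses p = π(1 − f); a count of grade 3 or higher uses p = π. The documents give neither π nor f for this regimen in this population, so both are assumed and varied.

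| Total rate π | f = 0% (also the result if grade 4 is counted) | f = 25% | f = 50% |
|---|---|---|---|
| 20% | 0.121 | 0.050 | 0.013 |
| 30% | 0.350 | 0.169 | 0.050 |
| 40% | 0.618 | 0.350 | 0.121 |

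For example, π = 30% and f = 25% give p = 0.30 × 0.75 = 0.225 and P(stop) = 0.169. In each row the literal rule is less likely to stop as more of the same number of severe events are grade 4. That direction does not depend on the values chosen; the size does.

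**A low grade 4 rate.** Section 2.4.1 reports 102 patients on brentuximab vedotin alone at 1.8 mg/kg, with grade 3 sensory neuropathy in 5% and no neuropathy among the listed grade 4 related events. Zero of 102 has a one-sided 95% upper limit of 1 − 0.05^(1/102) = 2.9%. Now assume 20% grade 3 plus 1% to 3% grade 4:

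- as written, p = 0.20 and P(stop) = 0.121;
- counting grade 4 as well, p = 0.21 to 0.23 and P(stop) = 0.139 to 0.179.

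**After the change.** With the event defined as grade 3 or higher and a 10% reference rate for that event, P(X ≥ 4) is again 0.0128.

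**The case against.** The strongest reply is that the gap is mostly theoretical, for three reasons.

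- The text does not expressly exclude grade 4. It counts participants who experience grade 3 neurotoxicity, and someone who passes through grade 3 on the way up or down has done so. Table 5-A acts on brentuximab vedotin from grade 2, so grade 4 with no recorded grade 3 phase should be uncommon.
- The documents' own data suggest that grade 4 neuropathy is rare. Besides the 102 monotherapy patients, the interim combination data in Section 2.4.2 do not list neuropathy among grade 3/4 events seen in more than 10% of patients.
- Grade 4 events would not go unseen. There is expedited reporting, adverse event review on monthly calls and by the Medical Monitor, termination on request under 4.7.2, and in France an IDMC whose first meeting can be triggered by a neurologic serious event.

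Much of this stands. It limits the claim to participants recorded only at grade 4 and makes large effects unlikely if grade 4 is rare. It does not remove the gap. The general condition asks for grade 3 lasting more than 4 weeks, so a participant who worsens quickly to grade 4 may not meet it. The monotherapy study had no vinblastine and a different schedule. None of the oversight routes counts grade 4 events against a boundary fixed in advance.

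A reader might also infer two stronger things that the documents do not support. One is that the rule weakens whenever toxicity worsens. It does not: if the grade 3 rate rises from 20% to 30%, the literal stopping probability rises from 0.12 to 0.35. The weakening holds only with the total rate of grade 3 or higher held fixed. The other is that this is the trial's only quantitative toxicity boundary. Phase I has a DLT count per dose level (Section 4.1), and 4.7.1 item 2 stops the trial at a single PML case with CD4 above 50.

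**Conclusion.** The point holds as a defect in the event definition. As worded in both protocols, the rule gives no basis for counting a participant recorded only at grade 4, and nothing else in the documents supplies one. Grade 3 or higher may well have been meant, but that is not written.

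The size depends on an unknown grade split. It is modest if grade 4 is rare (0.12 against 0.14 to 0.18 in the low-rate case). It is material if a quarter to a half of severe events are grade 4 (0.35 falling to 0.17 or 0.05 at a 30% total rate). These figures assume independent participants with a common rate and no grade 3 record for those at grade 4; any such record moves the literal result towards the full count. The stated false-stop probability is correct and is not in dispute.

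**What to change.** In AMC Section 4.7.1 item 1 and French Section 13.4 item 1, replace grade 3 by grade 3 or higher in every sentence: the general condition, the boundary and the probability statement. State that each participant is counted once. The cost is a few words in each protocol. The boundary, the 10 participants monitored and the printed bound of 5% all stay as they are, and no dose or individual treatment rule is touched.

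Two other mismatches in the same item should be reconciled separately. A trigger of more than 10% of participants is not the same threshold as more than 3 of 10, and the 4-week duration in the general condition is missing from the boundary sentence.

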5.0 DOSE MODIFICATIONS/TOXICITY MANAGEMENT

5.1 Brentuximab Vedotin Dose Modifications

Intrapatient Dose Reductions for Starting Dose of 1.2 mg/kg Every 2 Weeks.

No further dose reductions will be permitted beyond 0.6 mg/kg of brentuximab vedotin. Participants not tolerating a dose of 0.6mg/kg will continue with standard dose AVD at the discretion of the investigator.

Dose Level
1.2 mg/kg
0.9 mg/kg
0.6 mg/kg

Table 5-A: Treatment Modification Guidelines for Brentuximab Vedotin for All Cycles

Event	CTCAE v5.0	Action to be Taken	
	Grade		
Allergic reactions, or	Grade 1-2	For first reaction:	
Acute infusional		• Hold the infusion and wait 30 to 60 minutes	
reactions/ cytokine		(depending upon the reaction severity).	
release syndrome		 (depending upon the reaction severity). Treat reactions with diphenhydramine 1 mg/ (max 50 mg), or follow local instituti guidelines. Depending on the reaction severi dexamethasone 0.2mg/kg (max 10mg) IV show be used or follow local institution guidelines. Upon resolution of the symptoms, at a physician's discretion, it may be possible resume treatment by administering an H2 bloch approximately 30 minutes before restarting a infusion. Acetaminophen can also be considered Brentuximab vedotin may be administered at h of the previously administered rate at a discretion of the investigator. 	
		 For subsequent doses: Utilize diphenhydramine with or without acetaminophen as pre-treatment for all subsequent infusions. Dosing will be administered over the shortest infusion period that was well tolerated. If Grade 1-2 infusion reactions recur despite the above measures, either during re-challenge or subsequent treatments: 	

Event	CTCAE v5.0	Action to be Taken	
	Grade		
		 Take the measures outlined above. With subsequent dosing, add dexamethasone 0.2 mg/kg (max 10mg) IV or equivalent to medications above prior to infusion. 	
	Grade 3	 Stop infusion immediately. Administer diphenhydramine hydrochloride 1 mg/kg IV (max 50 mg), dexamethasone 0.2mg/kg (max 10mg) IV (or equivalent), bronchodilators for bronchospasms, and other medications as medically indicated. Once symptoms recover, brentuximab vedotin should not be resumed for that course. Subsequent courses of brentuximab vedotin may be considered at physicians' discretion. All subsequent infusions will use the following premedications prior to infusion, diphenhydramine hydrochloride 1 mg/kg IV (max 50 mg), dexamethasone 0.2mg/kg (max 10mg) IV (or equivalent). In addition, the infusion will be administered at 50% of the previous infusion rate. 	
	Grade 4	 Stop infusion immediately. Administer diphenhydramine hydrochloride 1 mg/kg (max 50mg) IV, dexamethasone 0.2 mg/kg (max 10mg) IV (or equivalent), and other anaphylaxis medications as indicated. Epinephrine or bronchodilators at the discretion of the investigator will be administered as indicated. Hospital admission for observation may be indicated Discontinue brentuximab vedotin. 	
Anaphylaxis	Any grade	If anaphylaxis occurs, immediately and permanently discontinue administration of brentuximab vedotin and administer appropriate medical therapy.	
Pancreatitis	Grade 2	 Withhold dose until toxicity has returned to baseline, then continue on protocol therapy but resume at one dose reduction. If Grade 2 pancreatitis recurs after one dose reduction, the participant must be removed from protocol therapy. 	
	Grades 3-4	Permanently discontinue brentuximab vedotin.	
Peripheral	Grade 1	Continue at same dose level.	

Event	CTCAE v5.0	Action to be Taken	
	Grade		
Neuropathy	Grade 2	 Treatment is to be delayed until neuropathy improves to Grade 1 or baseline. Brentuximab vedotin will be reduced by one dose level for subsequent treatments once peripheral neuropathy returns to baseline or returns to a grade 1. Participants who experience a delay of over 7 days in cycle 1 will be removed from the study. For subsequent cycles, if two sequential doses of brentuximab vedotin are held due to unresolved toxicity, leading to a treatment delay of an additional 2 weeks (i.e., 4 weeks between doses), participants will have the option to discontinue protocol therapy or continue study with AVD with dose adjustments in vinblastine as clinically necessary based on the level of neuropathy on the day of treatment as per standard label/summary product characteristics. 	
	Grade 3	 Treatment is to be delayed until neuropathy improves to Grade 1 or baseline. Brentuximab vedotin will be reduced by one dose level for subsequent treatments once peripheral neuropathy returns to baseline or returns to a grade 1. Participants who develop grade 3 neuropathy after dose reduction will have to discontinue brentuximab vedotin. Participants will have the option to be taken off protocol or continue study with AVD with dose adjustments as clinically necessary. Participants who experience a delay of over 7 days in cycle 1 will be removed from the study. For subsequent cycles, if two sequential doses of brentuximab vedotin are held due to unresolved toxicity, leading to a treatment delay of an additional 2 weeks (i.e., 4 weeks between doses), the participants will discontinue brentuximab vedotin. Participants will have the option to discontinue protocol therapy or continue study with AVD with dose adjustments in vinblastine as clinically necessary, based on the level of neuropathy on the day of treatment as per standard label/Summary product characteristics. 	

Event	CTCAE v5.0	Action to be Taken	
	Grade		
	Grade 4	Discontinue brentuximab vedotin.	
Neutropenia	Grade 1-2	Continue at same dose level.	
Occurring on the Day of Treatment ^b	Grade 3-4	 Reinstitute growth factor support (GCSF) for treatment of neutropenia until recovery to ANC ≥1,000/mm³. If myeloid growth factor support was inadvertently omitted in the previous dose, participants should receive the same full dose of brentuximab vedotin in the next treatment dose, along with myeloid growth factor support. If, as per protocol, the participant was on myeloid growth factor support with the previous dose and presents with treatment day neutropenia, reinstitute daily growth factor support (GCSF) until recovery to ANC ≥1,000/mm³ and reduce brentuximab vedotin one dose level for all remaining cycles. Dose reduction below brentuximab vedotin 0.6 mg/kg is not allowed. Brentuximab vedotin should not be given for any subsequent cycles. 	
Thrombocytopenia	Grade 1-2	Continue at same dose level.	
	Grade 3-4	 Withhold dose until toxicity is ≤ Grade 2 or has returned to baseline, then continue on protocol therapy but at one dose reduction. Participants who experience Grade 3-4 thrombocytopenia after dose reduction must be removed from protocol therapy. Participants who experience a delay of over 7 days in cycle 1 will be removed from the study. For subsequent cycles, if two sequential doses of brentuximab vedotin are held due to unresolved toxicity, leading to a treatment delay of an additional 2 weeks (i.e., 4 weeks between doses), the participant will be taken off protocol therapy. 	
Lymphopenia	Grade 1-4	Continue at same dose level.	

Event	CTCAE v5.0	Action to be Taken	
	Grade		
Non-hematologic ^a	Grade 1-2	Continue at same dose level.	
events (not including electrolyte abnormalities or febrile neutropenia) (See Section 5.1.3 for treatment modifications for febrile neutropenia)	Grade 3-4	 Continue at same dose level. Withhold dose until toxicity is ≤ Grade 2 or h returned to baseline, then continue on protoco therapy but resume at one dose reduction brentuximab vedotin. If non-hematological Grade 3-4 toxicity recurafter one dose reduction, the participant must removed from protocol therapy. Participants who experience a delay of over days in cycle 1 will be removed from protocol therapy. For subsequent cycles, if two sequent doses of brentuximab vedotin are held due unresolved toxicity, leading to a treatment del of an additional 2 weeks (i.e., 4 weeks betwee doses), the participants will be taken off protocol therapy, and brentuximab vedotin will discontinued. Participants will have the option be taken off protocol or continue study with j AVD without brentuximab vedotin. 	
Electrolyte Abnormalities	Grade 1-4	 Continue at same dose level, provided electrolyte toxicity is not medically consequential and has been readily corrected. If electrolyte abnormality is medically consequential, refer to guidelines above for non-hematologic events. 	

^a Participants who develop Grade 3 or 4 electrolyte laboratory abnormalities may continue study treatment without interruption but should receive appropriate medical therapy at the discretion of the investigator. ^b See Section 4.4.1 for instructions on GCSF supportive treatment.

5.1.1 Dose Modifications for Progressive Multifocal Leukoencephalopathy (PML)

PML is a rare demyelinating disease of the brain that is caused by the John Cunningham virus (JCV). It typically occurs in immunocompromised individuals and can be fatal. Presenting features may include altered mental status, motor deficits such as hemiparesis or ataxia, visual disturbances, or higher cortical dysfunction such as dysphasia or agnosia. Seizures have also been reported in PML patients (approximately 20%). Cognitive decline without accompanying deficits in motor or sensory function is uncommon. Optic nerve involvement, fever, and spinal cord disease are not typically associated with PML. In addition, peripheral neuropathy, which has been reported with brentuximab vedotin treatment, is not commonly reported with PML.

If PML is suspected, a diagnostic work-up must be performed. The work-up may include, but is not limited to the following:

• Neurologic examinations and neurology consultation, as warranted.

- Brain MRI. Features suggestive of PML include presence of unifocal or multifocal lesions, mainly of the white matter, which are typically non-enhancing and do not have mass effect.
- PCR analysis. JCV DNA, detectable in CSF or in a brain biopsy, is suggestive of PML.

Brentuximab vedotin dosing must be held if PML is suspected. If PML is confirmed, brentuximab vedotin must be permanently discontinued.

5.1.2 Dose Modifications for Pulmonary Toxicity

Pulmonary toxicity will be defined by grade 3 or 4 dyspnea, pneumonitis, and/or hypoxia that persists for at least three days. There must be no evidence of other etiologies, including left atrial hypertension, congestive heart failure, infection, metabolic abnormalities, or cancer related causes (e.g., malignant pericarditis).

Participants who develop pulmonary toxicity associated with brentuximab vedotin may benefit from treatment with corticosteroids. However, there are no published guidelines to suggest the most appropriate dosing or duration of treatment. Administration of 100 mg of oral or intravenous prednisolone in single daily or two divided doses has been reported to improve symptoms in adults with pulmonary toxicity secondary to gemcitabine. The suggested dose for participants who develop pulmonary toxicity is methylprednisolone 1 mg/kg IV every 12 hours for a minimum of seven days. Participants who develop pulmonary toxicity meeting the above definition will be taken off protocol therapy (brentuximab vedotin).

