4.6 Criteria for Permanent Removal from Treatment

After enrollment, participants will be permanently withdrawn from study treatment for any of the following reasons. In the event of withdrawal from treatment, the reason for study treatment removal and the date the participant was removed must be documented in the Off Protocol Treatment Form in AdvantageEDCSM. See Section 8.4 on evaluations to be performed at early discontinuation of therapy.

4.6.1 Participants who experience a delay of over 7 days in cycle 1 will be removed from protocol therapy. For subsequent cycles, if two sequential doses of AVD + BV or AVD alone are held due to unresolved toxicity, leading to a treatment delay of an
additional 2 weeks (i.e., 4 weeks between doses), the participant will be taken off protocol therapy. The participant will be followed for survival and may resume AVD treatment off study.

- 4.6.2 Severe toxicities as outlined in Section 5.0.
- 4.6.3 Progressive lymphoma at any time while on study.
- 4.6.4 Voluntary withdrawal.
- 4.6.5 The investigator has the right to remove participants from study for clinical reasons which he or she believes to be life threatening or resulting in significant morbidity to the participant.
- 4.6.6 Any participant who develops HBV reactivation or acute Hepatitis B as defined by the reappearance of a previously suppressed hepatitis B surface antigen, a positive IgM hepatitis B core antibody, and a positive viral load. Any participant with Hepatitis B or C who has worsening liver function as defined by Section 5.2.5 will also be removed from study.
- 4.6.7 Participants who become pregnant or breast-feed.
- 4.6.8 Participants with progressive disease at the end of cycle 2 will be removed from study treatment, while participants with stable disease may be removed from the study treatment at the discretion of the local responsible investigator. Progressive or stable disease defined at cycle 2 will be based by CT criteria only, as FDG-PET has yet to be validated in HIV-associated HL.
- 4.6.9 If found by central pathology review to not have the diagnosis of HIV-HL.

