	Grade 3-4	 Reinstitute growth factor support (GCSF) for treatment of neutropenia until recovery to ANC ≥1,000/mm3. If myeloid growth factor support was inadvertently omitted in the previous dose, patients should receive the same full dose of brentuximab vedotin in the next treatment dose, along with myeloid growth factor support If, as per protocol, the participant was on myeloid growth factor support with the previous dose and presents with treatment day neutropenia, reinstitute myeloid growth factor support (GCSF) until recovery to ANC ≥1,000/mm3 and reduce brentuximab vedotin one dose level for all remaining cycles. Dose reduction below brentuximab vedotin 0.6 mg/kg is not allowed. Brentuximab vedotin should not be given for any subsequent cycles. If participants have febrile neutropenia, please see Section 10.6 for dose modifications.
Thrombocytopenia	Grade 1-2	Continue at same dose level.
	Grade 3-4	 Withhold dose until toxicity is ≤ Grade 2 or has returned to baseline, then continue on protocol therapy but at one dose reduction Patients who experience Grade 3-4 thrombocytopenia after dose reduction must be removed from protocol therapy Patients who experience a delay of over 7 days in cycle 1 will be removed from the study. For subsequent cycles, if two sequential doses of brentuximab vedotin are held due to unresolved toxicity, leading to a treatment delay of an additional 2 weeks (i.e., 4 weeks between doses), the patient will be taken off protocol therapy.
Lymphopenia	Grade 1-4	Continue at same dose level.
Non-hematologic ^a events (not including electrolyte abnormalities) or febrile neutropenia) (See Section 10.6.1.5 for treatment modifications for febrile neutropenia)	Grade 1-2	Continue at same dose level.

Event	CTCAE.v4.0 Grade	Action to be Taken

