	Grade 3-4	 Withhold dose until toxicity is ≤ Grade 2 or has returned to baseline, then continue on protocol therapy but resume at one dose reduction of brentuximab vedotin. If non-hematological Grade 3-4 toxicity recurs after one dose reduction, the patient must be removed from protocol therapy Patients who experience a delay of over 7 days in cycle 1 will be removed from the study. For subsequent cycles, if two sequential doses of brentuximab vedotin are held due to unresolved toxicity, leading to a treatment delay of an additional 2 weeks (i.e., 4 weeks between doses), the patients will be taken off protocol therapy, and brentuximab vedotin will be discontinued. Participants will have the option to be taken off protocol or continue study with just AVD without brentuximab vedotin.
Electrolyte Abnormalities	Grade 1-4	 Continue at same dose level, provided electrolyte toxicity is not medically consequential and has been readily corrected If electrolyte abnormality is medically consequential, refer to guidelines above for non-hematologic events

^a Patients who develop Grade 3 or 4 electrolyte laboratory abnormalities may continue study treatment without interruption but should receive appropriate medical therapy at the discretion of the investigator.

^b GCSF will be administered on Days 2-10 and 16-24 throughout each 28-day cycle using standard doses. Pegfilgrastim may be substituted for GCSF and administered on days 2 and 16.

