10.6.1.4 Dose Modifications for Pulmonary Toxicity

Pulmonary toxicity will be defined by grade 3 or 4 dyspnea, pneumonitis, and/or hypoxia that persists for at least three days. There must be no evidence of other etiologies, including left atrial hypertension, congestive heart failure, infection, metabolic abnormalities, or cancer related causes (e.g., malignant pericarditis).

Patients who develop pulmonary toxicity associated with brentuximab vedotin may benefit from treatment with corticosteroids. However, there are no published guidelines to suggest the most appropriate dosing or duration of treatment. Administration of 100 mg of oral or intravenous prednisolone in single daily or two divided doses has been reported to improve symptoms in adults with pulmonary toxicity secondary to gemcitabine. The suggested dose for patients who develop pulmonary toxicity is methylprednisolone 1 mg/kg IV every 12 hours for a minimum of seven days. Patients who develop pulmonary toxicity meeting the above definition will be taken off protocol therapy.

See Section 13.1 for a complete listing of potential adverse events and Section 13.1.1 for special precautions and safety issues.

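### In both protocols the grade 3-4 non-hematologic row, read literally, restarts brentuximab vedotin after lung toxicity that the pulmonary subsection says must end it; neither that subsection nor the PML one has a table row or pointer

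*Combined protocol and SAP*

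**What the plan says.** **Table row.** In AMC Table 5-A (Section 5.1) the last general row covers non-hematologic "events (not including electrolyte abnormalities or febrile neutropenia", followed by a pointer to Section 5.1.3. The French table in 10.6.1.2 has the same exclusions and a single pointer: "See Section 10.6.1.5 for treatment modifications for febrile neutropenia". At grade 3-4 both tables hold the dose until the toxicity falls to grade 2 or lower or to baseline, and "then continue on protocol therapy but resume at one dose reduction of brentuximab vedotin" (French wording; the AMC row gives the same action). The row removes the participant only if the toxicity recurs after a reduction or the delay exceeds a limit.

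**Pulmonary subsection.** AMC 5.1.2 and French 10.6.1.4 define pulmonary toxicity as grade 3-4 dyspnea, pneumonitis or hypoxia persisting at least three days without another cause. AMC: "Participants who develop pulmonary toxicity meeting the above definition will be taken off protocol therapy (brentuximab vedotin". French: "Patients who develop pulmonary toxicity meeting the above definition will be taken off protocol therapy". Neither offers a restart.

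**PML subsection.** AMC 5.1.1, repeated as French 10.6.1.3, holds dosing on suspicion, and "If PML is confirmed, brentuximab vedotin must be permanently discontinued".

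**Related rules.** AMC 5.1 sets a floor: "No further dose reductions will be permitted beyond 0.6 mg/kg of brentuximab vedotin". AMC 4.6.2 lists as a ground for permanent removal "Severe toxicities as outlined in" Section 5.0, and French 13.1 item 2 does the same for Section 10.6.1.

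**The concern.** Every lung event that meets the 5.1.2 definition is also a grade 3-4 non-hematologic event, so a first event receives two different instructions: restart lower, or stop. The drafters saw that a toxicity handled outside the table needs an exclusion and a pointer, because they supplied both for febrile neutropenia. Pulmonary toxicity and PML received neither, and neither has a row of its own. Someone working from the table, which is titled as applying to all cycles, sees no sign that a stricter rule exists.

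At stake is re-exposure of a participant to brentuximab vedotin after lung injury with no other identified cause. The trigger for a restart is plausible. Section 5.1.2 suggests at least seven days of corticosteroid, and Section 6.1.1 reports that most patients with lung toxicity on brentuximab vedotin plus ABVD responded to steroids. That setting included bleomycin, so the evidence is indirect. Improvement to grade 2 is what the row treats as permission to resume.

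**Working it through.** The plan states no figure for this point, so the check is mainly a comparison of rules.

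**Rule check.** Take a first grade 3 pneumonitis at 1.2 mg/kg that lasts at least three days, has no other cause, and improves to grade 2 within the permitted delay.

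| Source | Action on brentuximab vedotin |
|---|---|
| Non-hematologic row, AMC Table 5-A and French 10.6.1.2 | Hold, then resume at 0.9 mg/kg |
| AMC 5.1.2 and French 10.6.1.4 | Stop |
| AMC 4.6.2 and French 13.1 item 2 | Permanent removal for severe toxicities under a section that contains both rules above |

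The removal criteria lean toward stopping, but they refer to the whole dose-modification section and do not state precedence.

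**Toxicities handled outside the table.**

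| Toxicity | Subsection (AMC / French) | Excluded by the row, with pointer? |
|---|---|---|
| PML | 5.1.1 / 10.6.1.3 | No |
| Pulmonary toxicity | 5.1.2 / 10.6.1.4 | No |
| Febrile neutropenia | 5.1.3 / 10.6.1.5 | Yes |

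So 1 of 3 is excluded. Electrolyte abnormalities are excluded too, but they have their own table row.

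**Where the conflict does not arise.** Lung events shorter than three days, or with another cause, fall under the row alone. A participant already at 0.6 mg/kg cannot be reduced further. The conflict therefore concerns qualifying events at 1.2 or 0.9 mg/kg.

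**How many participants.** The risk table in AMC 6.1 (n = 798, brentuximab vedotin trials, not specific to the AVD combination) places pulmonary toxicity in its <3% column. Using 3% as an assumed upper value:

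- All phase II: 0.03 × 51 = 1.53
- France: 0.03 × 20 = 0.60

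Both are before the grade, duration and etiology conditions, so the working range is 0 to 1.53 of 51. The 3% is an assumption and not a strict bound, because dyspnea as a single term sits in a more frequent column that is not split by grade or cause.

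**How far apart the rules are for one participant.**

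- Planned doses: 6 cycles × 2 = 12
- Event after dose 4: row allows up to 12 − 4 = 8 more; 5.1.2 allows 0
- Event after dose 1 (worst case): row allows up to 12 − 1 = 11 more; 5.1.2 allows 0
- Reduced dose on restart from 1.2 mg/kg: 0.9 / 1.2 = 75%

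The 11-dose case also requires recovery within the cycle 1 delay limit and no recurrence afterwards.

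**The case against.** The strongest reply is that the specific rule plainly governs. Section 5.1.2 is mandatory, has its own definition and title, and follows the table in the same chapter. The row is a residual category that already yields elsewhere: read literally it would also restart the drug after grade 3-4 pancreatitis, for which the table orders permanent discontinuation. Febrile neutropenia needed an express exclusion because its rule can be more lenient (a first episode may keep the same dose); a stricter rule can operate on top of a general one without it. Other safeguards exist as well: 24-hour reporting of serious grade 3-5 events, medical monitor review, monthly calls on adverse events, and investigator discretion to withdraw.

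Most of this stands and limits the size of the point. It does not remove it. Pancreatitis, neuropathy and infusion reactions have rows in the same table, so a table reader is redirected; pulmonary toxicity and PML have no row and no pointer. The precedence argument helps only a reader who looks past the table. The safeguards make a wrong restart likely to be noticed, but none is written to prevent it. France adds a withdrawal rule for DLCO below 70% (13.1 item 7), yet on-treatment lung function tests are scheduled only at cycles 3 and 5. The AMC schedule lists none.

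A reader might also infer that the two countries stop different things, because the AMC sentence names brentuximab vedotin in parentheses and the French one does not. The documents do not settle that. French 10.6.1.4 sits under a heading on brentuximab vedotin dose modifications, and the French pulmonary row in 10.6.2 makes DLCO a condition for continuing brentuximab vedotin, while French 9.4 and 13.1 item 7 read more broadly. Adding the parenthesis to the French text would narrow a safety stop with no clinical reason given.

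**Conclusion.** The inconsistency is real and present in both protocols: followed literally, the dose table gives the wrong action for a first qualifying lung event, and no sentence states which rule prevails. It is a low-frequency patient-safety matter. Fewer than 1.53 of 51 participants would be involved under the assumed 3%, and harm would require a site to use the table without the subsection.

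Three stronger readings are not supported. The protocols do not authorize re-exposure after lung toxicity, since the specific stop very probably governs. The roughly 40% lung toxicity rate in Section 6.1.1 cannot size the problem, because it comes from a bleomycin-containing combination; the same section says monotherapy carries no clinically meaningful lung risk, although a footnote to the risk table records pulmonary toxicity in monotherapy trials. Nothing here shows an effect on the two-year PFS estimate. For PML the practical gap is smaller still, because a case with CD4 above 50 also terminates the trial (AMC 4.7.1, French 13.4).

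**What to change.** In the non-hematologic row of both tables, extend the exclusions and place the cross-references beside the existing one for febrile neutropenia:

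- AMC Table 5-A: also exclude pulmonary toxicity meeting Section 5.1.2, and suspected or confirmed PML (Section 5.1.1).
- French 10.6.1.2: also exclude pulmonary toxicity meeting Section 10.6.1.4, and suspected or confirmed PML (Section 10.6.1.3).

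Leave the closing sentence of French 10.6.1.4 as it is. The change is two phrases and two pointers per table, made through the ordinary amendment process. It alters no visit, sample size or analysis.
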